1. PROGRAM SUMMARY

Please provide a brief summary of your grant project including the needs to be addressed, the services provided, and the population served.

Gentle Warriors Academy (GWA) is designed to help urban community adult fathers age 18 and older with dependent child(ren) up to 24 years of age incorporate practices and behaviors for managing the responsibilities of being parents/co-parents and partners through responsible parting, healthy marriage/relationships, economic stability activities, and grant-funded participation supports through a 40-hr/10-week cohort-based approach. These core areas are reinforced through GWA's coordinated case management process and wrap-around services, which is tailored to help address obstacles that fathers and their families face on their journeys to attaining and maintaining healthy parental and partner relationships as well as program completion.

Fathers Incorporated utilizes a skills-based curricula for its core GWA services: Next Level Fatherhood which was created and tailored by subject matter experts and Fathers Incorporated practitioners/staff to address the complex challenges and needs of urban community fathers. All curricula consist of 10 modules of learning that are designed to develop practical and comprehensive skillsets that are transferrable throughout all aspects of life.

The objectives of the Next Level Fatherhood curriculum are to: 1. Provide participants with practical skills necessary to navigate critical aspects of responsible fatherhood, healthy marriages, and personal/family economic stability; 2. Provide participants with tools that will assist them in strengthening their marriages, child engagement, and co-parenting relationships, and to provide information and resources around viable economic stability for themselves and their families; 3. Provide participants with skills necessary to making better and more informed parenting choices, to be more pro-active and less reactive, and to strengthen parental relationships; and 4. Encourage participants to become more acutely aware of how they present themselves in the lives of their children, significant others, and in the "systems" (family court, judicial court, child support, state agencies etc.) in which they have to navigate.

Participating fathers will work with Case Managers to review the results of all assessments and to determine necessary support services through the duration of program participation. Case Managers will implement case management best practices, record case notes that document interaction/support provided to all participants and will ensure that each participant receives six hours of dedicated case management from program enrollment through completion. Certified Life Coaches will work in tandem with Case Managers to help participants obtain and reach their goals, promote, and develop their strengths, and to overcome difficult challenges, specifically within their marriages or other significant relationships, their economic viability and their parental responsibilities as identified through co-developed Individual Success Plans (ISPs).

2. EVALUATION GOALS

Please briefly describe key goals of your evaluation and what you hope to learn below.

In this evaluation, it is anticipated that participants will show an increase in:

- Communications and handling conflict and other related relationship skills
- Understanding in role as a father
- Improved communication with partner/co-partner
- Understanding the quality of father-child engagement
- Various forms of contact with children

3. EVALUATION ENROLLMENT

Please provide the expected start and end dates for program and evaluation enrollment using the tables below. For impact studies, please indicate expected start and end dates for each study group.

DESCRIPTIVE EVALUATION		
Please leave blank if not conducting a descriptive outcome evaluation.		
	Program Enrollment	Study Enrollment
Start Date	4/1/2021	4/1/2021
End Date	7/1/2025	3/31/2024
Definition	All program participants who enroll in services	All program participants who consent to being part of the study

4. EVALUATION TIMELINE

Please include a timeline for key activities of the evaluation below. Example of activities may include IRB submission, staff training, waves of data collection, analysis period, and report writing and submission.

Evaluation Activity	Start Date	End Date
Additional Evaluation staff hiring and onboarding	1/15/2021	2/15/2021
Evaluation staff training	1/22/2021	2/20/2021
Evaluation Kickoff meeting and orientation with all program staff	2/2/2021	2/3/2021
IRB training and certification by all program and evaluation staff	10/1/2020	2/28/2021
Development and submission of Evaluation Plan document	1/15/2021	2/19/2021
Evaluation Tools Development	10/1/2021	2/28/2021
IRB Approval	3/1/2021	3/15/2021
IRB Full Board Approval	05/11/2023	06/01/2024
IRB Approval for Incarcerated Population	06/02/2023	06/01/2024
CQI Team Formed and Meeting bi-weekly	3/15/2021	7/1/2025
Training for CQI Team	3/15/2021	3/28/2021
Training for all Program Staff on Research Methods and process	3/15/2021	3/28/2021
Implementation Evaluation Data Collection	4/1/2021	8/15/2025
-Baseline	4/1/2021	7/1/2025
-Post Test	5/15/2021	8/15/2025
-Follow-up	4/1/2021	8/15/2025
1 st Manuscript submitted for publication	7/1/2025	9/30/2025

Final Descriptive Report Submitted

9/1/2025

9/29/2025

* you may add rows by hitting the tab button, or right click and select insert row below

EVALUATION PLAN

1. RESEARCH QUESTIONS

1.1. OVERVIEW OF RESEARCH QUESTIONS

Please state the research question(s) that the evaluation intends to answer and for each research question indicate the type: implementation or outcome.

- *Implementation Questions: Identifying whether a program has been successful in attaining desired implementation goals (e.g., reaching intended target population, enrolling intended number of participants, delivering training and services in manner intended, etc.)*
- *Outcome Questions: Identifying whether program is associated with intended outcomes for participants (e.g., do participants' knowledge, attitudes, behaviors, or awareness change?)*

Research questions in this study are framed by a Descriptive Evaluation Design to assess whether outcomes improve for low-income fathers who participate in the Gentle Warriors Academy (GWA) Project. Primary outcomes are assessed before and after participants complete core curricula—*Next Level Fatherhood*—and *Case Management* and *Certified Life Coaching* as support services (pre to post). Primary outcomes will indicate whether behavior improved for healthy family relationships (parent, co-parent, and partner). See Table 1 below.

No	Research Question	Implementation or Outcome?
R1	Will participants report significantly healthier parenting behavior after completing primary educational services and employment support services?	Primary Outcome
R2	Will participants report significantly healthier parenting attitudes after completing primary educational services and employment support services?	Primary Outcome

R3	Will participants report significantly healthier co-parenting behavior after completing primary educational services and employment support services?	Primary Outcome
R4	Will participants report significantly healthier partner relationship behavior after completing primary educational services and employment support services?	Primary Outcome

* you may add rows by hitting the tab button, or right click and select insert row below

1.2. OUTCOME RESEARCH QUESTIONS

For each outcome research question listed above, whether a descriptive or impact design, summarize the inputs (e.g., program components, program supports, implementation features, etc.), target population (e.g., the population for which the effect will be estimated) and the outcomes (e.g., child well-being, father-child engagement, etc.) that will be examined to answer the research question(s). Comparisons for descriptive evaluations may reflect circumstances before the grant, pre-treatment, or pre-determined benchmark from other studies with similar interventions.

Research Question Number Should correspond to the number indicated in Table 1.1 above	Intervention Program component or set of activities that the evaluation will test or examine	Target Population Population for which the effect of the treatment will be estimated	Comparison What the intervention will be compared to (e.g., pre-intervention for descriptive designs)	Outcome Changes that are expected to occur as a result of the intervention	Confirmatory or Exploratory? Confirmatory: those upon which conclusions will be drawn Exploratory: those that may provide additional suggestive evidence
R1	Primary curricula (Next Level Fatherhood); Support Services (Case Management, Life Coaching);	Urban fathers who are 18+ years with children up to 24 years	Assessment of healthy parenting behavior at GWA Project enrollment.	Participants who complete primary and support services will report healthier parenting behavior	Confirmatory

	Continuous Quality Improvement (CQI) Process			one year after GWA Project enrollment.	
R2	Primary curricula (Next Level Fatherhood); Support Services (Case Management, Life Coaching); Continuous Quality Improvement (CQI) Process	Urban fathers who are 18+ years with children up to 24 years	Assessment of healthy parenting attitudes at GWA Project enrollment.	Participants who complete primary and support services will report healthier parenting attitudes one year after GWA Project enrollment.	Confirmatory
R3	Primary curricula (Next Level Fatherhood); Support Services (Case Management, Life Coaching); Continuous Quality Improvement (CQI) Process	Urban fathers who are 18+ years with children up to 24 years	Assessment of healthy co-parenting behavior at GWA Project enrollment.	Participants who complete primary and support services will report healthier co-parenting behavior one year after GWA Project enrollment.	Confirmatory
R4	Primary curricula (Next Level Fatherhood); Support Services (Case Management, Life Coaching); Continuous Quality	Urban fathers who are 18+ years with children up to 24 years	Assessment of healthy partner relationship behavior at GWA Project enrollment	Participants who complete primary and support services will report healthier partner relationship behavior one year after GWA	Confirmatory

Improvement (CQI) Process	Project enrollment.
---------------------------	---------------------

* you may add rows by hitting the tab button, or right click and select insert row below

2. BACKGROUND

For each outcome research question listed in 1.1, whether descriptive or impact design, briefly summarize the previous literature or existing research that informs the stated research question and how the evaluation will expand the evidence base. Explain why the research questions are of specific interest to the program and/or community. Only a short summary paragraph description is needed below. Additional documentation, such as a literature review, may be appended to this document.

Research Question Topic	Existing Research	Contribution to the Evidence Base	Interest to the Program and/or Community
R1 and R2	Low-income fathers can lack the parenting skills to fulfill their familial obligations as a parent to promote healthy family relationships.	Determine the extent to which the delivery of GWA Project services enhance the parenting skills of low-income fathers.	Inform practitioners about whether GWA Project design promotes healthy family relationships by improving parent behavior .
R3	Low-income fathers can lack the co-parenting skills to fulfill their familial obligations as a parent to promote healthy family relationships.	Determine the extent to which the delivery of GWA Project services enhance the co-parenting skills of low-income fathers.	Inform practitioners about whether GWA Project design promotes healthy family relationships by improving co-parent behavior .
R4	Low-income fathers can lack the relationship skills to fulfill their obligations as a partner to promote healthy family relationships.	Determine the extent to which the delivery of GWA Project services enhance the partner relationship skills of low-income fathers.	Inform practitioners about whether GWA Project design promotes healthy family relationships by improving partner relationship behavior .

* you may add rows by hitting the tab button, or right click and select insert row below

3. HYPOTHESES

For each specified research question, state the hypothesized result(s) and briefly describe why these results are anticipated.

Research Question	Hypothesized Result
R1	Participants will report healthier parenting behavior after the complete primary services and employment support services in the GWA Project.
R2	Participants will report healthier parenting attitudes after the complete primary services and employment support services in the GWA Project.
R3	Participants will report healthier co-parenting behavior after the complete primary services and employment support services in the GWA Project.
R4	Participants will report healthier partner relationship behavior after the complete primary services and employment support services in the GWA Project.

* you may add rows by hitting the tab button, or right click and select insert row below

4. RESEARCH DESIGN

For each research question, briefly describe why the research design proposed will answer each research question(s). State whether the proposed evaluation is a descriptive or impact evaluation and justify why the proposed research design is best suited to answer the research question(s).

Research Question	Design	Justification
R1	Pre to post outcomes assessment of GWA participation for healthy parenting behavior .	Healthy change reported by participants in their parenting behavior from pre to post estimates the maximum amount of benefit that can be attributed to GWA services in the absence of a counterfactual.
R2	Pre to post outcomes assessment of GWA participation for healthy parenting attitudes .	Healthy change reported by participants in their parenting attitudes from pre to post estimates the maximum amount of benefit that can be attributed to GWA services in the absence of a counterfactual.
R3	Pre to post outcomes assessment of GWA participation for healthy co-parenting behavior .	Healthy change reported by participants in their co-parenting behavior from pre to post estimates the maximum amount of benefit that

		can be attributed to GWA services in the absence of a counterfactual.
R4	Pre to post outcomes assessment of GWA participation for healthy partner relationship behavior .	Healthy change reported by participants in their partner relationship behavior from pre to post estimates the maximum amount of benefit that can be attributed to GWA services in the absence of a counterfactual.

* you may add rows by hitting the tab button, or right click and select insert row below

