Gentle Warriors Academy Healthy Marriage and Responsible Fatherhood Program Evaluation

4/22/2024

Clinicaltrials.gov ID: NCT06899100

Statistical Analysis Plan

1. Data Analysis

Briefly describe the planned approach for data analysis. If an impact analysis is proposed, name the key dependent and independent variables, and describe any methods to minimize Type I error (i.e., finding positive impacts by chance) such as limiting the number of impacts to be analyzed and/or multiple comparison correction. Describe proposed approach(es) for addressing missing data.

Analytic Sample

The study sample includes participants who: 1) gave recorded informed consent to be part of the study, and 2) took both an entrance and exit survey. The analytic sample for particular outcome measure will vary based on missing data.

Outcome measures

For each outcome construct, we have identified the relevant measures from nFORM and the OLLE survey that are theoretically aligned with that construct. We will generate a correlation matrix between items in a given construct to ensure that theoretically related items are also empirically related in our data set. Items that are not strongly correlated with other items in a construct will be removed as necessary. Factor analysis will be used to ensure that all construct items hang together (using an alpha of 0.7 or higher as the threshold).

Once we are confident that all of the items align with a given construct, we will create a composite measure by taking an average of the scores on each non-missing item in the construct. The measure definition matrix below provides information on each proposed outcome. For composite measures, a change score will be calculated between a participant's pre-program composite score and post-program follow-up composite score. For standalone survey items, a change score will be calculated between a participant's pre-survey and follow-up survey responses.

For the sake of consistency and simplicity, parenting and co-parenting analyses will use a participant's youngest child as the focal child.

Construct	Sample	Measure	Data source(s)	Variable Name
Parenting Attitudes (toward children)	Has at least one child age 24 or younger	7 items: frequency of key attitudes (categories, 5-point scale)	nFORM entrance, OLLE follow-up	Copar_Att

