We will conduct response rate analysis for each primary outcome of interest to assess non-response bias and adjust for threats to internal validity. Using data from the Applicant Characteristics Survey, we will look at demographics (race, ethnicity, age, education level) and primary reason for joining the program among participants who fall into each of the following categories: 1) non-respondents who answered no surveys after the ACS, 2) respondents who completed the pre-survey only, 3) respondents who completed the post-survey only, and 4) respondents who completed both the pre- and follow-up survey (complete case).

Subgroup Analyses

We plan to compare data across two sets of subgroups. These are participants (fathers) whose ages range from 18-29 and those over the age of 30. We also plan to compare data across incarcerated participants and community participants.

Analytic approach

The main goal of this descriptive study is to assess pre-post change scores in the outcomes listed above among program participants before and after primary workshops. The changes will be assessed from program enrollment to one year after the enrollment (follow-up survey). We will use paired sample t-tests to assess the magnitude and significance of changes among program participants in the analytic sample for each outcome. We will adjust our p-values for multiple hypothesis testing and report the adjusted p-values in the appendix of the final report.

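### The protocol calls uncontrolled pre-post change the maximum benefit attributable to the program, but a single-group design gives no such bound

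*Protocol*

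**What the plan says.** Protocol Section 4 (Research Design) describes a one-group design; the entry for R1 is "Pre to post outcomes assessment of GWA participation for healthy parenting behavior". The justification column then says that healthy change reported by participants from pre to post "estimates the maximum amount of benefit that can be attributed to GWA services in the absence of a counterfactual". The same justification is given for R1, R2, R3 and R4, and it is the only one offered. Section 1.2 labels all four questions confirmatory.

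The comparator is each father's own starting point. For R1, Section 1.2 gives it as "Assessment of healthy parenting behavior at GWA Project enrollment".

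The SAP (Analytic approach) takes change from enrollment to the one-year follow-up and states: "We will use paired sample t-tests to assess the magnitude and significance of changes among program participants in the analytic sample for each outcome". It describes its purpose more modestly: "The main goal of this descriptive study is to assess pre-post change scores in the outcomes listed above among program participants". The analytic sample is consented participants who "took both an entrance and exit survey".

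Protocol Section 2 (Background) says that the evaluation will establish how far GWA services improve fathers' parenting, co-parenting and partner relationship skills. That is causal language.

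**The concern.** A maximum is a property that a design either has or lacks. A single-group pre-post comparison has it only under an assumption about what would have happened to the same fathers without the program. If outcomes would have worsened, the program's effect is larger than the observed change and the stated ceiling is too low. If outcomes would have improved, the observed change overstates the effect.

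What is at stake is the conclusion. A small or null change could be misread as a ceiling on what the program can achieve, and a positive change as benefit that the program produced. Neither follows from the data that this design collects.

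**Working it through.** The documents give no sample size, effect size or standard deviation for this point, so there is no stated figure to reproduce. The check is an identity, with outcomes signed so that positive means healthier:

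observed mean change = program effect + untreated change

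Hence observed change ≥ program effect if and only if untreated change ≥ 0.

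**Step 1. Is the condition stated or supported?** No section says that outcomes would stay flat or improve without the program. Time trend and regression to the mean are not discussed. The one planned bias check is the SAP's response-rate analysis, which compares respondent groups and says nothing about untreated change. A paired t-test on change from a father's own baseline cannot separate the two terms.

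**Step 2. What happens when the condition fails?** The values below are assumptions, in standard deviation units, with a true effect of +0.20.

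| Untreated change | Observed change | Is observed ≥ effect? |
|---|---|---|
| -0.30 | 0.20 - 0.30 = -0.10 | No |
| -0.10 | 0.20 - 0.10 = +0.10 | No |
| 0 | +0.20 | Yes, equal |
| +0.10 | 0.20 + 0.10 = +0.30 | Yes, overstated |
| +0.30 | 0.20 + 0.30 = +0.50 | Yes, overstated |

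The same identity read backwards, for an assumed observed change of +0.1 point: an untreated change of -0.2 gives an effect of 0.1 - (-0.2) = +0.3, and an untreated change of +0.2 gives 0.1 - 0.2 = -0.1.

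**Step 3. Is downward change plausible here?** For parenting behavior (R1), the SAP's missing-data section sets responses to Never (1) when the father has not seen his child in the past month, and keeps him in the analysis. Suppose a net share m of fathers lose contact between waves for reasons unrelated to the program, their baseline mean is b on the 1 to 5 scale, and the others do not change. The mean then moves by -m × (b - 1).

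| m (assumed) | b = 3 (assumed) | b = 4 (assumed) |
|---|---|---|
| 5% | -0.05 × 2 = -0.10 | -0.05 × 3 = -0.15 |
| 10% | -0.10 × 2 = -0.20 | -0.10 × 3 = -0.30 |
| 20% | -0.20 × 2 = -0.40 | -0.20 × 3 = -0.60 |

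This treats the outcome as a mean of 5-point items; the hours item is left aside. It also takes the missing-data rule as the operative one, although the SAP's measure table restricts the parenting behavior sample to fathers who saw the child within the past month.

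**Step 4. Is upward change plausible too?** Yes. Fathers may enroll at a low point and drift back toward their usual level. The analytic sample is also limited to those with both surveys, and Protocol Section 8.4 says that the post-program survey reaches only those who complete the program and attend that session. Change among completers can be more favorable than among all who enrolled.

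**The case against.** The sentence carries its own caveat: it says that there is no counterfactual. It can be read as a warning that at most this much should be credited to the program, which is a guard against over-claiming. The SAP calls the study descriptive and claims no bound, and Protocol Section 1.1 declares a descriptive design. This stands in part. The missing control is disclosed and the declared framing is modest. But the sentence still calls the change a maximum and speaks of benefit attributed to services. The caveat does not supply the missing condition, and the SAP does not correct the wording.

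Three further limits stand. The document-based route to decline concerns parenting behavior. For attitudes (R2) and the item on feeling overwhelmed (R4), the general logic applies but no specific downward mechanism has been shown. The numbers are hypothetical: they show that the bound can fail, not that it does fail here. And the Outcome column heading in Section 1.2, which speaks of changes resulting from the intervention, is form text and should not be cited as the sponsor's claim.

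A reader might infer that the final report will present a small change as a cap on benefit, or a gain as proven benefit. No reporting rule, threshold or success criterion in either document says so.

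**Conclusion.** The justification for R1 to R4 is wrong as written. Pre-post change in one group is an upper bound on benefit only if untreated change is zero or positive; this is assumed silently, and for parenting behavior the scoring rule makes it doubtful. The error equals the untreated change, in either direction, and this study cannot estimate it.

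The defect is one of interpretation. It would go too far to say that the paired analysis is invalid: as a description of how participants' reports changed, it stands, and no estimate, test or p-value is affected. It would also go too far to say that the change will overstate or understate the effect, because the documents do not settle the direction. The conclusion rests on the identity above and on the absence of any stated assumption about untreated change; it does not depend on the illustrative values.

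**What to change.** In Protocol Section 4, replace the justification for each of R1 to R4 with wording such as: *Pre-post change describes how participants' reports changed. Without a comparison group it neither identifies nor bounds the program effect, because trend, regression to the mean and selective completion can bias it in either direction.*

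In Protocol Section 2, change the statements about how far services enhance skills to statements about change observed among participants. Limit the conclusions of the final report to association, which matches the declared descriptive design.

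The cost is editing only: no new data and no change to the analysis. The downside is that the study's claim becomes weaker.
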